5. TABLE OF EVENTS

Table 4: Table of Events

	Screening Period					Tre	eatment Peri	od				Follow-up P	eriod
Events			(C 1-			C 3-6 (±3 days)		≥ C7 (±3 days)			90 days (+3)	SPM follow- up every 6 months (±2 weeks) after
	-28 to -1	D 1	D 2 ^g	D 8	D 15	D 22	D 1	D 15	D 1	EOT (≤7 days from trt discon decision)	28 days (+3) after EOT	after last DURVA/ DARA dose	weeks) after 90 day follow-aup visit
STUDY ENTRY AND GEN	VERAL ASSE	SSME	ENTS										
Informed consent	X	-	-	-	-	-	-	-	-	-	-	-	-
Inclusion/exclusion criteria	X	-	-	-	-	-	-	-	-	-	-	-	_
IRT registration	X	X	-	-	-	-	-	-	-	X	-	-	-
Complete medical history	X	-	-	-	-	-	-	-	-	-	-	-	-
Demographics	X	-	-	-	-	-	-	-	-	-	-	-	-
Prior disease history	X	-	-	-	-	-	-	-	-	-	-	-	-
Prior disease therapies	X	-	-	-	-	-	-	-	-	-	-	-	-
Forced expiratory volume test (subjects with COPD)	X	-	-	-	-	-	-	-	-	-	-	-	-
Prior/concomitant medication evaluation	X (-28 days from screening)		Coi	ntinuo	ous, un	til 90 da	ays after last o	dose of I	OURVA o	or DARA, wl	hichever is	later	-

Table 4: Table of Events (Continued)

	Screening Period					Tre	eatment Per	iod				Follow-up l	Period
Events		C 1-2 (±3 days)					C 3-6 (±3 days)		≥ C7 (±3 days)		28	90 days (+3) after	SPM follow- up every 6 months (±2
	-28 to -1	D 1 ^b	D 2 ^g	D 8	D 15	D 22	D 1	D 15	D 1	EOT (≤7 days from trt discon decision)	days (+3) after EOT	last DURVA/ DARA dose	weeks) after 90 day follow-up visit ^a
Blood Type, Rh, and IAT	-	X	-	-	-	-	-	-	-	-	-	-	-
SAFETY ASSESSMENTS													
Prior/concomitant procedures evaluation	X (-28 days from screening)		Continuous, until 90 days after last dose of DURVA or DARA, whichever is later								-		
AE evaluation	Continuo	ıs star	starting after informed consent signature, until 90 days after last dose of DURVA or DARA, whichever is later							-			
Monitoring for SPMs only for subjects receiving POM as part of study treatment	-	Co	ontinuo	ous fr	om firs	t dose o	of POM to th	e end of	trial (once	last subject	completes	the 90-day fo	ollow-up visit)
Physical examination	X	X	-	-	-	-	X	-	X	X	-	-	-
Vital signs	X	X	X	X	X	X	X	X	X	X	X	X	-
Height	X	-	-	-	-	-	-	-	-	-	-	-	-
Weight	X	X	X	X	X	X	X	X	X	X	X	X	-
12-lead ECG	X	C1	-	-	-	-	C6	-	-	X	-	-	-
Hepatitis and HIV testing	X	-	-	-	-	-	-	-	-	-	-	-	-
Hematology ^h	X	X	X	X	X	X	X	X	X	X	X	X	-

Table 4: Table of Events (Continued)

	Screening Period					Tre	eatment Per	riod				Follow-up P	Period
Events			(C 1- (±3 da)				C 3-6 (±3 days)				90 days (+3) after	SPM follow- up every 6 months (±2

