7.2.1. Treatment Administration

On days when DARA and DURVA are dosed on the same day, the DARA infusion should be administered first, followed by the DURVA infusion.

On days when DARA, DURVA and POM are dosed on the same day, the DARA infusion should be administered first, followed by the DURVA infusion, then POM administration.

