7.2.2. Treatment Schedule

7.2.2.1. Daratumumab Plus Durvalumab Treatment Schedule

Initial dosing will begin with Cohort 1. See section 3.1 for dosing rules.

- Intravenous DARA at the dose depending on the assigned cohort: Cycles 1 to 2 on Days 1, 8, 15, 22, Cycle 3 to 6 on Days 1 and 15, then on Day 1 for Cycle 7 onward of a 28-day cycle
 - Cohort 1: 16 mg/kg
 - Cohort -1: 16 mg/kg
- Intravenous DURVA at the dose depending on the assigned cohort on Day 2 of Cycle 1, then Day 1 of Cycle ≥ 2 of a 28-day cycle. For all DURVA infusion after Cycle 1, a +1 day window is allowed (subject may either receive the DURVA infusion on same day as the DARA infusion or on the next day per the investigator's discretion).
 - Cohort 1: 1500 mg
 - Cohort -1: 750 mg

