9.9. Safety Analysis

All safety analyses will be conducted using the Safety Population. All analyses will be presented by dose cohort and arm.

Adverse events will be coded according to the MedDRA Version 18 or higher. The intensity of AEs will be graded according to the NCI CTCAE Version 4.03 or higher.

Treatment-emergent AEs are defined as AE occurring or worsening on or after the first treatment of the study treatment and within 90 days after last dose of durvalumab. Treatment-emergent AEs, AEs leading to study treatment discontinuation, AEs leading to dose reduction/interruption, AEs related to study treatment, SAEs, and AEs leading to death will be summarized by system organ class, and preferred term for each treatment arm and dose cohort. A summary of AEs with

NCI CTCAE Grade 3 or higher, as well as the most frequent preferred terms, and AESIs will be provided. A summary of AEs by dosing cycle based on onset date will also be provided.

If a subject experiences the same preferred term multiple times then, the event will be counted only once and by greatest severity.

All deaths and reasons for death will be summarized. Deaths within 90 days after the last dose of durvalumab will be summarized separately.

Clinical laboratory values will be graded according to NCI CTCAE Version 4.03 or higher for applicable tests. Baseline grade and worst grade during treatment for selected laboratory results will be summarized. Shift from baseline to the worst grade observed during the treatment for selected laboratory results will also be provided.

For vital signs, shift from baseline to worst during the treatment in below, within, and above the normal ranges will be displayed in cross—tabulations. Summary statistics (N, Mean, Standard Deviation, Median, Minimum, and Maximum) of observed and change from baseline values will be presented.

The overall ECG interpretation will be summarized by presenting the number and percentage of subjects with "Normal", "Abnormal, not clinically significant, and "Abnormal, clinically significant". Shifts from baseline to worst during the treatment in the overall ECG interpretation will be displayed in cross–tabulations.

The number of subjects who develop anti-drug antibody against durvalumab and/or daratumumab will be summarized.

Graphical displays will be provided where useful to assist in the interpretation of results.

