All AEs will be recorded by the Investigator from the time the subject signs informed consent until 90 days after the last dose of DURVA or DARA, whichever is later, as well as those SAEs made known to the Investigator at any time thereafter that are suspected of being related to study IPs (durvalumab, daratumumab, POM, dex). Adverse events and SAEs will be recorded on the AE page of the CRF and in the subject's source documents. All SAEs must be reported to Celgene Drug Safety within 24 hours of the Investigator's knowledge of the event by facsimile, or other appropriate method, using the SAE Report Form, or approved equivalent form.

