10.5. Reporting of Serious Adverse Events

Any AE that meets any criterion for an SAE requires the completion of an SAE Report Form in addition to being recorded on the AE page/screen of the CRF. All SAEs must be reported to

Celgene Drug Safety within 24 hours of the Investigator's knowledge of the event by facsimile, or other appropriate method (eg, via email), using the SAE Report Form, or approved equivalent form. This instruction pertains to initial SAE reports as well as any follow-up reports.

The Investigator is required to ensure that the data on these forms is accurate and consistent. This requirement applies to all SAEs (regardless of relationship to IPs [DARA, DURVA, POM, or dex]) that occur during the study (from the time the subject signs informed consent until 90 days after the last dose of DURVA or DARA, whichever is later) or any SAE made known to the Investigator at anytime thereafter that are suspected of being related to IPs (DARA, DURVA, POM, or dex). Serious adverse events occurring prior to treatment (after signing the ICF) will be captured.

The SAE report should provide a detailed description of the SAE and include a concise summary of hospital records and other relevant documents. If a subject died and an autopsy has been performed, copies of the autopsy report and death certificate are to be sent to Celgene Drug Safety as soon as these become available. Any follow-up data should be detailed in a subsequent SAE Report Form, or approved equivalent form, and sent to Celgene Drug Safety.

Where required by local legislation, the Investigator is responsible for informing the Institutional Review Board/Ethics Committee (IRB/EC) of the SAE and providing them with all relevant initial and follow-up information about the event. The Investigator must keep copies of all SAE information on file including correspondence with Celgene and the IRB/EC.

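### Section 9.9 ends the TEAE window and the 90-day death split on the last durvalumab dose, so collected follow-up falls outside whenever daratumumab is given last, and a daratumumab-only patient has no window end

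*Combined protocol and SAP*

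**What the plan says.** Section 9.9 defines a TEAE as an event "occurring or worsening on or after the first treatment of the study treatment and within 90 days after last dose of durvalumab". The same section asks for a summary of all deaths and, separately, of deaths up to 90 days from the last durvalumab dose.

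Collection runs on a different clock. Section 10.1 has AEs recorded "until 90 days after the last dose of DURVA or DARA, whichever is later". Section 10.5 sets the SAE period as running "from the time the subject signs informed consent until 90 days after the last dose of DURVA or DARA, whichever is later". The AE row of Table 4 (Section 5) runs "after informed consent signature, until 90 days after last dose of DURVA or DARA, whichever is later". The AE items in Sections 6.2.1 and 6.3.1 agree with these.

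The dosing schedule is in Section 7.2.2.1. DARA is given on "Cycles 1 to 2 on Days 1, 8, 15, 22, Cycle 3 to 6 on Days 1 and 15, then on Day 1" from Cycle 7 onward. For the other drug the text is "Intravenous DURVA at the dose depending on the assigned cohort on Day 2 of Cycle 1", then Day 1 of each later cycle, with the addition that "For all DURVA infusion after Cycle 1, a +1 day window is allowed". Section 7.2.1 sets the order: "On days when DARA and DURVA are dosed on the same day, the DARA infusion should be administered first, followed by the DURVA infusion".

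The Safety Population (Section 9.2) takes in anyone who had a dose of any study drug. Table 2 lists safety as a primary endpoint.

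**The concern.** The window opens on whichever drug is given first, which is DARA on Cycle 1 Day 1, and closes on DURVA alone. DURVA is given once at the start of each cycle, while DARA continues later in the cycle through Cycle 6. The last infusion a patient receives is therefore often DARA. In that case the final stretch of follow-up, which sites are required to collect, is not treatment-emergent by the definition in Section 9.9, purely because of which drug came last.

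This does not require an unusual course. The last scheduled infusion is DARA on Day 22 in Cycles 1-2 and on Day 15 in Cycles 3-6. Response is assessed on Day 1 from Cycle 2 (Section 6.4.5), and progression is a reason to stop (Section 11.1). A patient who takes every dose of one of these cycles and stops before the next Day 1 dose is affected.

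At stake is the completeness of the main safety table for a primary endpoint that concerns the combination, not durvalumab alone. There is also a definitional hole. A patient who had DARA on Cycle 1 Day 1 and never reached DURVA is in the Safety Population but has no date from which to count the 90 days.

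**Working it through.** The 90 days are a definition, so there is no plan figure to reproduce. The check is how far apart the two end dates lie.

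**Inputs.** The dosing days and the permitted DURVA Day 1 or 2 from Cycle 2 on come from Section 7.2.2.1, and the order of infusions from Section 7.2.1. The analysis window end (last DURVA + 90) is from Section 9.9, and the collection end (later of last DURVA and last DARA, + 90) from Section 10.1.

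**Formulas.** Study day of Cycle c Day x = 28(c - 1) + x. Gap = max(0, day of last DARA - day of last DURVA). The 90 days cancel, so the gap is the collected time beyond the window.

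**Results, nominal schedule, no DURVA hold**

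| Last dose received | Last DARA day | Last DURVA day | Gap (days) | Share of the 90 post-DARA days |
|---|---|---|---|---|
| Cycle 1 Day 8 / 15 / 22 DARA | 8 / 15 / 22 | 2 | 6 / 13 / 20 | 6.7% / 14.4% / 22.2% |
| Cycle 2 Day 8 DARA | 36 | 29 or 30 | 7 or 6 | 7.8% or 6.7% |
| Cycle 2 Day 15 DARA | 43 | 29 or 30 | 14 or 13 | 15.6% or 14.4% |
| Cycle 2 Day 22 DARA | 50 | 29 or 30 | 21 or 20 | 23.3% or 22.2% |
| Cycles 3-6 Day 15 DARA (e.g. Cycle 3) | 71 | 57 or 58 | 14 or 13 | 15.6% or 14.4% |
| Cycle 2 Day 1 DARA, that cycle's DURVA not given | 29 | 2 | 27 | 30.0% |
| Cycle 3 Day 1 DARA, that cycle's DURVA not given | 57 | 29 or 30 | 28 or 27 | 31.1% or 30.0% |
| Cycle 7 Day 1 DARA, that cycle's DURVA not given | 169 | 141 or 142 | 28 or 27 | 31.1% or 30.0% |
| Any cycle, no DARA after the last DURVA | - | - | 0 | 0% |
| Cycle 1 Day 1 DARA only | 1 | none | undefined | undefined |

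A patient who completes a cycle and stops before the next Day 1 has a gap of 20 days after Cycle 1, 20-21 after Cycle 2 and 13-14 after any of Cycles 3-6. From Cycle 7 DARA is given only on Day 1, so once that cycle's DURVA has followed, the gap is 0.

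Where there is a gap on this schedule, 90 - 28 = 62 to 90 - 6 = 84 of the 90 post-DARA days stay inside the window. The dosing and visit windows in Table 4 and Section 6.2 shift these figures by a few days.

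**Beyond the nominal schedule.** Section 7.2.4 stops all study drugs when DURVA is permanently discontinued, but its rules do not cover a temporary DURVA hold. Assume, for illustration only, that Cycle 2 DURVA is held and DARA continues. A last dose on Cycle 2 Day 22 gives 50 - 2 = 48 days. A last dose on Cycle 3 Day 1, before any further DURVA, gives 57 - 2 = 55 days. That leaves 42 and 35 of the 90 days inside.

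**After alignment.** If Section 9.9 used the later of the two drugs, the gap would be 0 in every row, and the DARA-only patient's window would end at last DARA + 90.

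**The case against.** The durvalumab anchor could be deliberate. Permanent DURVA discontinuation ends all study treatment (Section 7.2.4), so DURVA roughly marks the end of the regimen, and the AESIs are defined around durvalumab (Section 10.7). Part of this stands: it rules out long DARA-only treatment after permanent DURVA discontinuation. It does not remove the gaps within a cycle, because DARA may already have been given since the last DURVA dose. The documents give no rationale for the one-drug limit, and causality is assessed for all study drugs (Section 10.2.3).

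The effect may also be small. Analyses are descriptive (Section 9.1), and no dose decision or stopping rule uses the window. Enrollment is closed (Section 3.2), and patients still on uninterrupted treatment are probably past Cycle 6, where the usual gap is 0. This stands as a limit on size. The tables nevertheless cover the whole Safety Population, including anyone who stopped in Cycles 1-6. The DARA-only case needs a stop between Cycle 1 Day 1 and Day 2, so it should be uncommon, but the plan still needs a rule for it.

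A reader might go further and infer that late deaths or serious events disappear from the report. The documents do not support that. All deaths are summarized without a window. Section 9.9 does not expressly tie the summaries of SAEs, related AEs, discontinuations, dose reductions or interruptions, Grade 3 or higher events, AESIs or AEs leading to death to the TEAE window. Nor are data lost: the events are collected and remain in the database.

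**Conclusion.** The point holds. The analysis window in Section 9.9 and the collection period in Section 10.1 end on different doses whenever DARA is last, and no other section repairs this. The nominal gap is 6 to 28 days, on the assumption that scheduled doses are given on time and DURVA is not held. It would be wrong to read 28 days as a maximum, because a DURVA hold with DARA continued could exceed it. It would also be wrong to read the gap as confined to patients who stop mid-cycle or between two infusions, since completing any of Cycles 1-6 and stopping there is enough.

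The consequence is confined to the TEAE tables and the 90-day death split. The number of patients or events affected cannot be derived from the documents, and nothing in them shows that a safety conclusion would change. It should be fixed because safety is a primary endpoint, because the rule as written excludes follow-up that the protocol requires, and because DARA-only patients would otherwise be handled by an ad hoc programming choice.

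The 90-day visit in Section 6.3.1 is also timed on durvalumab alone, against either drug in the Protocol Summary, Section 3.2 and Table 4. Section 6.3.1 itself refers to Table 4, so this looks like a drafting slip and adds no weight.

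**What to change.** In Section 9.9, define both the TEAE window and the separate death summary as running from the first dose of any study drug to 90 days after the later of the last DURVA and last DARA doses, which matches the Section 10.1 limit. State whether the summaries of SAEs, related AEs, discontinuations, dose reductions or interruptions, Grade 3 or higher events, AESIs and AEs leading to death use the same window. Keep the separate analysis of data after POM + dex is added (Section 9.1), and say how the window applies to it.

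Reconcile the visit timing in Section 6.3.1 with the Protocol Summary, Section 3.2 and Table 4. The visit allows +3 days, so an event starting on days 91-93 would remain outside the aligned window, just as it is outside the Section 10.1 collection limit.

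The cost is a sentence or two in Section 9.9 and one in Section 6.3.1, with no new data. The documents do not say whether the tables are already programmed; if they are, the TEAE tables and the death split need a rerun. For every patient who received DURVA the aligned window ends on the same day or later, so TEAE counts can only stay the same or rise.

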9.10. Interim Analysis

The Phase 2 portion of this study uses the Simon's 2-stage design (Simon, 1989). Once the RP2D is confirmed after the safety run-in portion, a cohort of 32 subjects (including subject enrolled in the safety run-in portion) will be enrolled at the RP2D to determine the safety and preliminary efficacy of D². If there are 11 or fewer responses in these 32 subjects (11/32=34.4%), the study will be stopped. Otherwise, 68 additional subjects will be accrued for a total of 100.

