By my signature, I indicate I have reviewed this protocol and fin	d its content to be acceptable.	

SITE PRINCIPAL INVESTIGATOR SIGNATURE PAGE

Signature of Site Principal Investigator	dd mmm yyyy	
Printed Name of Site Principal Investigator		
Institution Name:		
By my signature, I agree to personally supervise the conduct of this study at my study site and to ensure its conduct is in compliance with the protocol, informed consent, Institutional Review Board (IRB)/Ethics Committee (EC) procedures, instructions from Celgene representatives, the Declaration of Helsinki, International Council for Harmonisation (ICH) Good Clinical Practices Guidelines, and local regulations governing the conduct of clinical studies.		

COORDINATING PRINCIPAL INVESTIGATOR SIGNATURE PAGE

Signature of Coordinating Principal Investigator	dd mmm yyyy
Printed Name of Coordinating Principal Investigator	
Institution Name:	
By my signature, I agree the protocol has been written to comply Practices guidelines and agree to offer guidance throughout the s	

PROTOCOL SUMMARY

On 05 Sep 2017, a Partial Clinical Hold was placed on this study by the United States (US) Food and Drug Administration (FDA). The decision by the FDA was based on data related to risks of anti-programmed cell death-1 (PD-1) antibody, pembrolizumab, in combination with immunomodulatory drugs (IMiDs®) in patients with multiple myeloma. As a result, enrollment into this study has been discontinued. Subjects who are receiving clinical benefit, based on the discretion of the investigator, may remain on study treatment after being reconsented.

Study Title

A Phase 2, Multicenter, Open-label, Study to Determine the Safety and Efficacy for the Combination of Durvalumab (DURVA) and Daratumumab (DARA) (D²) in Subjects with Relapsed and Refractory Multiple Myeloma (RRMM)

Indication

Multiple myeloma with at least 3 prior therapies including a proteasome inhibitor (PI) and an immunomodulatory agent or double-refractory to a PI and an immunomodulatory agent.

Objectives

Primary: To determine the safety and efficacy of D^2 in subjects with RRMM Secondary:

- Evaluate additional measures of efficacy (time-to-response, duration of response, progressive-free survival) of D² in subjects with RRMM
- Evaluate the pharmacokinetics (PK) of DURVA and DARA in subjects with RRMM

Study Design

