- Clinical laboratory evaluations
- Pregnancy testing/counseling
- Electrocardiogram (ECG)
- Concomitant medications and procedures
- Adverse events (AEs)
- Second primary malignancies

Pharmacokinetic

 Serum/plasma samples will be collected to assay plasma concentrations of DURVA and DARA

Other

• Eastern Cooperative Oncology Group (ECOG) Performance Status

Statistical Methods

Simon's 2-stage design (Simon, 1989) will be used. The null hypothesis that the true overall response rate (ORR) is < 30% will be tested against a one-sided alternative. In the first stage, 32 subjects will be accrued. If there are 11 or fewer responses in these 32 subjects (11/32 = 34.4%), the study will be stopped. Otherwise, 68 additional subjects will be accrued to a total of 100. The null hypothesis will be rejected if 39 or more responses are observed in 100 subjects (39/100 = 39%). This design yields a Type I error rate of 0.05 and power of 80% when the true overall response rate is 45%. All analyses will use descriptive statistics. No formal statistical comparison/testing will be performed.

TABLE OF CONTENTS

TITLE P.	AGE	1
PROTOC	COL SUMMARY	6
1.	INTRODUCTION	18
1.1.	Disease Background	18
1.2.	Compound Background	18
1.2.1.	Durvalumab (MEDI4736)	18
1.2.2.	Daratumumab	19
1.2.3.	Pomalidomide	19
1.3.	Rationale	19
1.3.1.	Study Rationale and Purpose	19
1.3.2.	Rationale for the Study Design	20
1.3.4.	Rationale for Choice of Combination Compounds	22
1.5.4.	Rationale for Choice of Combination Compounds	
2.	STUDY OBJECTIVES AND ENDPOINTS	24
3.	OVERALL STUDY DESIGN	26
3.1.	Study Design	26
3.1.1.	D ² Arm	
3.1.1.1.	D ² Safety Run-In Phase	26
3.1.1.2.	D ² Phase 2 Portion	27
3.1.1.3.	Addition of Pomalidomide Plus Dexamethasone to Daratumumab Plus Durvalumab Upon Progressive Disease	27
3.1.3.	Dose Review Team.	27
3.1.4.	Dose-limiting Toxicity.	
3.2.	Study Duration for Subjects	
3.3.	End of Trial	
1	STUDY POPUL ATION	33

Durvalumab (MEDI4736)

Protocol 1	MEDI4736-MM-003	Celgene Corporation
4.1.	Number of Subjects	33
4.2.	Inclusion Criteria	33
4.3.	Exclusion Criteria	34
5.	TABLE OF EVENTS	38
6.	PROCEDURES	45
6.1.	Screening Period.	45
6.2.	Treatment Period	47
6.2.1.	End of Treatment	48
6.3.	Follow-up Period	49
6.3.1.	Safety Follow-up	49
6.3.2.	Second Primary Malignancy Follow-up	50
6.4.	Efficacy Assessments	50
6.4.1.	Laboratory Assessments for Efficacy Parameters	50
6.4.2.	Bone Marrow Aspiration and/or Biopsy	51
6.4.3.	Bone Lesion Assessment	51

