3.1.1.2. D^2 Phase 2 Portion

The Phase 2 will use a Simon 2-stage design to determine the efficacy and safety of D² (Simon, 1989).

D² Simon Stage 1

Once the RP2D is confirmed, a cohort of 32 subjects (including subject enrolled in the safety run-in portion) will be enrolled at the RP2D to determine the safety and preliminary efficacy of D^2 .

D² Simon Stage 2

If the threshold for minimum overall response rate (ORR) is met in Stage 1, an additional 68 subjects will be enrolled to further confirm the safety and efficacy of D² at the RP2D.

3.1.1.3. Addition of Pomalidomide Plus Dexamethasone to Daratumumab Plus Durvalumab Upon Progressive Disease

For all subjects enrolled into D^2Arm , upon confirmed PD, for subjects who have had at least 2 cycles of D^2 , POM + dex may be added to the D^2 regimen at the investigator's discretion.

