9. STATISTICAL CONSIDERATIONS

9.1. Overview

All analyses will use descriptive statistics. The analyses will be done by cohorts and arms. Subjects treated with the recommended dose in the Phase 2 portion of D^2 will be combined with the corresponding dose cohort in the safety run-in phase as one single dose cohort for efficacy and safety analysis. Safety and efficacy data for subjects after addition of POM + dex following confirmed PD will be analyzed separately.

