9.3. Sample Size and Power Considerations

Sample size for D^2 arm is calculated based on Simon's 2-stage design (Simon, 1989). The null hypothesis that the true overall response rate (ORR) is < 30% will be tested against a one-sided alternative. In the first stage, 32 subjects will be accrued. If there are 11 or fewer responses in these 32 subjects (11/32 = 34.4%), the study will be stopped. Otherwise, 68 additional subjects will be accrued to a total of 100. The null hypothesis will be rejected if 39 or more responses are observed in 100 subjects (39/100 = 39%). This design yields a Type I error rate of 0.05 and power of 80% when the true overall response rate is 45%.

Number of observed responses in 32 subjects	80% Confidence Interval
10/32	31.3% (20.4%, 44.0%)
11/32	34.4% (23.1%, 47.2%)
12/32	37.5% (25.9%, 50.4%)
13/32	40.6% (28.7%, 53.5%)
14/32	43.8% 31.6%, 56.6%)
15/32	46.9% (34.6%, 59.6%)
16/32	50.0% (37.4%, 62.6%)
17/32	53.1% (40.4%, 65.5%)
18/32	56.3% (43.4%, 68.4%)
19/32	59.4% (46.5%, 71.3%)
20/32	62.5% (49.6%, 74.1%)

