Appendix E (updated)

2. Appendix E-1: Durvalumab Treatment Modification and Toxicity Management Guidelines for Immune-mediated Adverse Events, was updated to match Durvalumab Toxicity Management Guidelines, Version 4.03, dated 17 Oct 2019 and Durvalumab IB Version 15 dated 08 Oct 2019.

Protocol Amendment 2 is written to update the Toxicity Management Guidelines (TMGs) and to reflect that on 05 Sep 2017 the United States (US) Food and Drug Administration (FDA) placed a Partial Clinical Hold on this study. The decision by the FDA was based on risks identified in other trials for an anti-programmed cell death-1 (PD-1) antibody, pembrolizumab, in patients with multiple myeloma in combination with immunomodulatory agents.

Significant changes included in this amendment are summarized below:

Discontinuation of enrollment of new subjects

- Only those subjects already enrolled and treated who are receiving clinical benefit, based on the discretion of the investigator, can remain on treatment after being informed and reconsented on the safety concerns with the combination of a programmed cell death-1 (PD-1) pathway inhibitor and an immunomodulatory agent.
- Changes to the protocol have been made in the Protocol Summary, Section 1 and Section 3.2 to reflect discontinuation of enrollment.

Updates to the Toxicity Management Guidelines (TMGs)

• Updates have been made to the general dose modification and TMGs in Appendix E-1 to include revised Durvalumab Toxicity Management Guidelines.

Other changes:

• Correction of typographical errors and updated tables and table footnotes with revised text throughout the document.

Protocol Amendment 1.0 was written to

correct the dosing of daratumumab (DARA) in the protocol summary to correspond with Sections 7.2.2.1 and 7.2.2.1.1 of the protocol (the protocol summary incorrectly stated a dose level of DARA 8 mg/kg).

The amendment also includes several other updates, minor clarifications and corrections:

• Updated status of DARA regulatory approvals to include the European Union (Sections 1.2.2, 1.3.1, 1.3.4 and 7.2.1.2)

- Dose Review Team composition to include study specific consultants, as required (Protocol summary and Section 3.1.3)
- Includes a minimum number of doses of POM and dexamethasone (dex) for the dose limiting toxicity evaluation for subjects who receive POM + dex as part of their regimen. This is to ensure alignment with the other MEDI4736 protocols (Section 3.1.4).

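### The plan says both that the response rate will be tested against 30% and that nothing will be tested, and it keeps the 39/100 rule and 80% power after enrolment was closed

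*Combined protocol and SAP*

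**What the plan says.** **Tested or not.** The Protocol Summary, Statistical Methods, sets a null ORR below 30% against a one-sided alternative. It stops after Stage 1 at 11 or fewer responses in 32, and otherwise continues to 100. Section 9.3 gives the same design. In both places: "The null hypothesis will be rejected if 39 or more responses are observed in 100 subjects", and "This design yields a Type I error rate of 0.05 and power of 80% when the true overall response rate is 45"%. The Summary paragraph then closes with a sentence that all analyses are descriptive, followed by "No formal statistical comparison/testing will be performed". Section 9.1 opens with "All analyses will use descriptive statistics" and does not repeat the no-testing sentence.

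**Enrolment.** The opening of the Summary, Section 1 and Section 3.2 each report the partial clinical hold of 05 Sep 2017 and state "As a result, enrollment into this study has been discontinued".

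**Stage 2.** A Stage 2 of 68, conditional on passing Stage 1, remains in:
- the Summary (Study Design and Statistical Methods);
- 3.1.1.2, "an additional 68 subjects will be enrolled to further confirm the safety and efficacy";
- 4.1, which lists up to 68;
- 9.3;
- 9.10, "Otherwise, 68 additional subjects will be accrued for a total of 100".

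The rejection bound and the power appear only in the Summary and 9.3.

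**Estimation.** Section 9.8.1 defines the ORR as subjects with at least a partial response divided by the Efficacy Evaluable (EE) Population. It refers to a 95% confidence interval for subjects treated at the recommended phase 2 dose (RP2D).

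**The concern.** ORR is one of the two primary endpoints. It is investigator-assessed in an open-label study, so the basis for its conclusion should be fixed in writing and not left to be chosen once responses are known. A report author following 9.3 would declare the null rejected or not rejected; one following the last sentence of the Summary paragraph would report an estimate and make no such claim. Both would be following the plan.

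The closure of enrolment adds a second difficulty. Nothing in Section 9 mentions it or says how ORR will be judged on a sample other than 32 or 100. A reader could then quote 80% power for a sample that may not have it.

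**Working it through.** **1. The statements side by side**

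| Place | Null tested and rejected at 39/100 | Descriptive only | No formal testing |
|---|---|---|---|
| Summary, Statistical Methods | yes | yes | yes |
| 9.1 | – | yes | – |
| 9.3 | yes | – | – |
| 9.10 | – (stopping rule and accrual only) | – | – |

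The conflict lies within one paragraph of the Summary, and again between 9.1 and 9.3. It does not depend on the number enrolled.

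**2. The plan's own figure.** Inputs from 9.3: Stage 1 of 32, stop at 11 or fewer, total 100, reject at 39 or more, null 0.30, alternative 0.45. The exact probability of rejection is

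Rej(N, r, p) = sum over x = 12 to 32 of P(Bin(32, p) = x) × P(Bin(N − 32, p) ≥ r − x).

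- Rej(100, 39, 0.45) = 0.8001, so the stated 80% reproduces.
- Rej(100, 39, 0.30) = 0.0247. The attained one-sided error is about 0.025, half the stated 0.05.
- Rej(100, 38, 0.30) = 0.0364 and Rej(100, 38, 0.45) = 0.8185. So 39 is the smallest bound within 0.025, but not the smallest within 0.05.
- The probability of stopping after Stage 1 is 0.772 at a true ORR of 30% and 0.151 at 45%.

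**3. If accrual stopped between 32 and 100.** The documents do not give the number enrolled, so N is an assumption here. The 11/32 rule is kept, and r is the smallest bound with Rej(N, r, 0.30) ≤ 0.025, the level the planned rule attains.

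| N | Bound | Attained error | Power at 45% |
|---|---|---|---|
| 100 | 39 | 0.0247 | 80.0% |
| 90 | 36 | 0.0213 | 77.0% |
| 80 | 33 | 0.0176 | 72.2% |
| 70 | 29 | 0.0236 | 71.2% |
| 60 | 26 | 0.0181 | 62.6% |

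With a ceiling of 0.05 instead, the bound at N = 90 is 34 with power 81.9%. That is above the planned 80.0% only because the error is allowed to rise to 0.0477. At N = 70 the bound of 28 gives 76.2%, at an error of 0.0383. These figures should not be set against the planned rule.

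**4. If accrual stopped before Stage 1 was full.** Neither stated bound can be applied. As an illustration, a single-stage exact test with one-sided error of at most 0.05 has power 25.3% at N = 18 (10 or more responses) and 38.5% at N = 24 (12 or more).

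**5. What estimation would give.** The exact (Clopper-Pearson) two-sided 95% interval is 29.4% to 49.3% at 39/100 and 30.3% to 50.3% at 40/100. At N = 100, therefore, the planned test and the interval disagree about 30% only at exactly 39 responses. That result has probability 2.6% at a true ORR of 45%. The 80% intervals tabulated in 9.3 also agree with the exact method: 12/32 gives 25.9% to 50.4%.

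**The case against.** The Stage 2 text can fairly be read as leftover planning text. The 68 subjects are conditional everywhere, the discontinuation notice opens both the Summary and Section 1, and 9.3 is a sample-size section whose power statement is correct for the design it describes. No site would take 9.10 as permission to enrol. Descriptive analysis (9.1) with an ORR and a 95% interval (9.8.1) already supplies most of an estimation plan. The no-testing sentence may have been meant for between-group comparisons.

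Much of this stands. It makes the enrolment part a matter of labelling and points to estimation as the natural remedy. It does not remove the contradiction. The Simon text is not marked as historical and is written as a rule still to be applied. The no-testing sentence is unrestricted and directly follows a hypothesis test.

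Four stronger inferences are tempting, and the documents do not support them:
- **That the trial was cut short and lost its test.** The number enrolled is not stated. A trial that stopped at 70 to 99 would need a new bound and a restated power, but would still have a test.
- **That 80% was miscalculated.** It reproduces.
- **That 12 or more responses in 32 would be reported as success.** Section 3.1.1.2 and 9.10 present Stage 1 as preliminary efficacy and a condition for continuing.
- **That 9.8.1 leaves the interval incomplete.** Its sentence is cut off in the text as read, so nothing follows from what it does not say.

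**Conclusion.** The point holds and should be corrected, at moderate weight. The testing contradiction is certain from the text and applies at any sample size. The mismatch with closed enrolment is also certain as text: the 39/100 bound and 80% power describe the trial only if 100 subjects were enrolled at the RP2D, or if Stage 1 ended with 11 or fewer responses in 32 and the design finished by its own rule.

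The size of any loss cannot be stated, because the number enrolled is not given. On the assumption of 60 to 90 subjects, with the 11/32 rule kept and error held to 0.025, power at a 45% ORR would be about 63% to 77%. It would be far lower only if accrual stopped during or soon after Stage 1. The stated Type I error of 0.05 also differs from the attained one-sided 0.0247. That errs on the cautious side, but it matters if a bound is ever re-derived.

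**What to change.** Changes of wording, in an amendment or a SAP:

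1. In the Summary and 9.3, label the Simon bounds, Type I error and 80% power as the original planning basis. Give the attained one-sided error as about 0.025, and say that the power does not apply to a truncated sample.
2. State one basis for the primary ORR conclusion, namely estimation: the 9.8.1 ORR in the EE Population treated at the RP2D, with an exact (Clopper-Pearson) 95% confidence interval. Remove the statements that the null will be tested and rejected as operative rules.
3. Add a cross-reference to the discontinuation in 3.1.1.2, 4.1, 9.3 and 9.10.

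The cost is the formal test and its stated power. At N = 100 little is lost, since the two approaches part only at 39 responses.

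If the sponsor prefers to keep a test, it must delete the no-testing sentence and reconcile 9.1. Any new bound must be set without sight of the responses, which is harder in an open-label study. It must also use the 9.8.1 denominator (the EE Population, not the number enrolled) and an error rate comparable to the planned rule. For example, 29/70 with the 11/32 rule kept has error 0.024 and power 71.2%.
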